#### 4.2.5.3 Efficacy analyses

The analyses of the efficacy endpoints, including the incidence of protocol-defined medically attended RSV LRTI (also described as the medically attended RSV LRTI) through 150 days post dose, as well as the incidence of protocol-defined RSV hospitalization (also described as the RSV LRTI hospitalization) through 150 days post dose. The incidence will be calculated as the proportion of subjects who meet the endpoint during the reporting period. Only summaries will be provided for the efficacy analyses unless stated otherwise. The summaries will be based on observed events.

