4.8.6 Efficacy

[figure not shown]
The incidence of medically attended RSV LRTI (inpatient and outpatient) through 150 days post dose, based on RSV test results (performed centrally using RT-PCR) and objective

protocol-defined LRTI criteria, will be summarized for all dosed subjects. For subjects with multiple medically attended RSV LRTI events, only the first occurrence will be used in the analysis.

The incidence of RSV hospitalization through 150 days after dose will also be summarized. Additional analyses will include summarizing RSV-positive LRTI endpoints using results from either the central laboratory or local laboratory.

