9 CHANGES TO THE PROTOCOL

At the time of the original protocol and Amendments 1 and 2, this study was planned to be conducted only in Japan. Amendments 1 and 2 are described below. Amendment 3, which revised the protocol for global use, is described before the Protocol Synopsis.

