## 2 ANALYSIS SETS

### 2.1 Definition of analysis set

The analysis sets defined in this study are the as-treated population and the as-treated Japan subpopulation. All analyses performed are to be conducted on these populations unless stated otherwise.

The as-treated population includes all subjects who are enrolled (once written informed consent is obtained) and received any dose of nirsevimab.

The as-treated Japan subpopulation is a subset of the as-treated population and includes only subjects who were enrolled in sites located in Japan.

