#### **4.1.5 Implementation of data cut-off (DCO) for interim analysis**

The principle is to only report the data collected up to the DCO date (16May2022) for the interim analysis.

- Partial dates will be imputed before applying DCO.
- Records with start date after DCO will be removed in SDTM datasets
- If end date is after DCO, then end date will be reset as missing, event status will be reset as ongoing in SDTM datasets if applicable.

The date of DCO is displayed in the header of tables, listings and figures for DCO applied outputs as: ‘Interim Analysis: Data cut-off = 16MAY2022’. If outputs are produced before IA a prefix is added as ‘Pre-’.

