#### **Analysis of incidence of medically attended LRTI due to RT-PCR-confirmed RSV**

An analysis window which captures all relevant respiratory samples that linked to respiratory illness events will be defined prior to database lock and the decision made will be documented. In addition, deaths that can be demonstrated as caused by RSV (by autopsy or clinical history and virologic evidence) will also be considered as medically attended RSV LRTI events.

The incidence of medically attended RSV LRTI (inpatient and outpatient) through 150 days post dose will be summarized, and a listing of subjects with medically attended RSV LRTI will also be provided. For subjects with multiple medically attended RSV LRTI events, only the first occurrence will be used in the summary.

In addition, the incidence of medically attended RSV LRTI that occurred after 150 days post dose, and through 360 days post dose will be summarized.

The incidence of medically attended RSV LRTI by subtype (RSV A or RSV B) through 150 days post dose, after 150 days post dose, and through 360 days post dose will be summarized.

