**Table 1 Population for medically attend RSV respiratory illness**

Type of Endpoint	Endpoint	Protocol definition of LRTI	RSV test result	Investigators assessment of LRTI/URTI	Setting of care
Secondary Efficacy	MA RSV LRTI	Protocol defined	Positive (central RT-PCR)	LRTI	Inpatient or outpatient
Secondary Efficacy	MA RSV LRTI with hospitalization	Protocol defined	Positive (central RT-PCR)	LRTI	Inpatient

CCI

[figure not shown]
All above stated summaries will be based on observed events and data summary will be presented through 150 days post dose, after 150 days post dose, and through 360 days post dose.

Adverse events associated with all medically attended RSV LRTI will be summarized, as well as categorized by the MedDRA SOC and PT. Summaries will be presented through 150 days post dose, after 150 days post dose, and through 360 days post dose.

[figure not shown]
To evaluate the impact of ADA on efficacy, MA LRTI and MA LRTI with hospitalization will be summarized by ADA post-baseline status (ie, at least one post-baseline ADA positive or not through 360 days post dose).

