#### **4.2.6.4 Healthcare resource utilization (HRU)**

Healthcare resource utilization will be measured as follows:

- Admissions to hospitals and duration of stay.
- Admissions to ICU and duration of stay.
- Requiring respiratory support (using initial/increased CPAP or initial/increased mechanical ventilation) and the duration of use.
- Uses and the duration of use of initial/increased supplemental oxygen.
- Visits to out-patient facilities (urgent care, outpatient ED, outpatient clinic).
- Prescription and OTC medications and duration of use.

These data will be provided through 360 days post dose and will be reported through 150 days post dose, after 150 days post dose, and through 360 days post dose.

Specifically, to report HRU, the following summaries will be repeated for the six endpoints described in [Table 1](#).

- The number and percent of subjects who have had at least one of the following: hospitalization, ICU admission, requiring respiratory support, requiring supplemental oxygen, or visiting an outpatient facility. Similar summaries will be provided by respiratory support subtype (initial/increased CPAP or initial/increased mechanical ventilation) and the type of outpatient facility. The percentage will be calculated for time interval through 150 days post dose, after 150 days post dose, and through 360 days post dose.
- For each of the medical activities listed above, the total number of the activity for a subject who has had at least one respective event in the reporting time-period will be calculated and summarized.
- The total duration of each of the following (in days) will be calculated cumulatively through 360 days post dose and summarized: hospital stay, ICU stay, use of respiratory support, or use of supplemental oxygen for the subjects who has had at least one of the corresponding activities.

The duration of each hospitalization will be calculated from the admission or deterioration date to discharge date. If the discharge date is missing because the subject died in the hospital, the duration of that hospital stay will be calculated from admission to the death date, or end-of-study date, whichever is the earliest. Total duration of hospitalization is the cumulated days of each hospital stay throughout the reporting time-period.

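### At interims triggered at Day 151, the readable SAP lets children whose follow-up window is still open count as event-free in the after-150-day and through-360-day RSV percentages; the first-interim population is also worded two ways

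*SAP*

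**What the plan says.** **Incidence.** SAP 4.2.5.3 states: "The incidence will be calculated as the proportion of subjects who meet the endpoint during the reporting period". The same paragraph bases the summaries on observed events.

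**Windows.** For medically attended RSV LRTI, the SAP adds to the 150-day result the incidence "that occurred after 150 days post dose, and through 360 days post dose will be summarized". RSV hospitalization has the same windows, and the text after Table 1 repeats them for all the efficacy summaries: "data summary will be presented through 150 days post dose, after 150 days post dose, and through 360 days post dose". For healthcare resource utilization (HRU), SAP 4.2.6.4 says: "The percentage will be calculated for time interval through 150 days post dose, after 150 days post dose, and through 360 days post dose".

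**Denominator.** SAP 2.1: "The as-treated population includes all subjects who are enrolled (once written informed consent is obtained) and received any dose of nirsevimab". SAP 4 applies this set unless stated otherwise. Protocol 4.8.6 says of the through-150-day endpoint that incidence, based on "protocol-defined LRTI criteria, will be summarized for all dosed subjects". SAP 4.2.1, however, counts children who completed Day 151 as those included in the efficacy evaluation.

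**Interims.** SAP 5.1 triggers the first interim when children enrolled by the end of 2021 have been followed through Day 151. SAP 5.2 adds a second, when all children enrolled globally have been followed through Day 151, with the same outputs. SAP 4.1.5: "The principle is to only report the data collected up to the DCO date (16May2022) for the interim analysis". It deletes records that start after the cut-off and resets later end dates. It says nothing about denominators.

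**First-interim population.** The Protocol synopsis and Protocol 4.8.8 analyse children enrolled by the end of 2021, and SAP 4.1 uses that phrase for the trigger. Protocol 4.8.1 and SAP 5.1 use it for the trigger too, but then analyse data for children enrolled in 2021.

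**The concern.** A crude proportion in all dosed children is sound when everyone has been followed to the end of the window, apart from dropout and death. An interim triggered at Day 151 meets that condition for the 150-day window. It does not for the other two: the most recently dosed children have hardly entered the after-150-day window and are well short of 360 days. They stay in the denominator and can add few or no events to the numerator, so the percentage can only be pulled down.

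An interim reader could then take a low or zero later-window figure as lasting protection when much of that follow-up has not yet happened. The interim is meant to support extrapolation of efficacy and safety, so its tables will be read.

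The population wording matters for a different reason: it changes who is analysed. Protocol 9 says that under the original protocol and Amendments 1 and 2 "this study was planned to be conducted only in Japan". Read literally, enrolment in 2021 leaves out any child enrolled in Japan before that year.

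**Working it through.** The plan gives no figure to reproduce: there is no event rate, accrual pattern or interim denominator. The check is calendar arithmetic, followed by an illustration on stated assumptions.

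**Step 1. Dates (no assumption needed).** The cut-off is 16 May 2022 (SAP 4.1.5). By the study-day rule in SAP 4.1.3, Day 151 is the dose date + 150 and Day 361 is the dose date + 360.

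- Latest dosing date with 360 days: 16 May 2022 − 360 d = 21 May 2021.
- Latest dosing date that reaches Day 151: 16 May 2022 − 150 d = 17 Dec 2021. With the 7-day visit allowance in Protocol Table 5: 16 May 2022 − 143 d = 24 Dec 2021.
- Longest follow-up for a child dosed on or after 23 June 2021, the date of the amendment that took the study beyond Japan: 327 d. No such child can have a closed 360-day window.

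**Step 2. Share of each window observed at the first interim.** Assumed: dosing dates uniform from a chosen start to 31 Dec 2021, and no dropout. Let u be the days from dosing to cut-off. The after-150-day window is 360 − 150 = 210 days long. The mean observed shares are:

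- after 150 days: mean of min(max(u − 150, 0), 210)/210
- through 360 days: mean of min(u, 360)/360
- through 150 days: mean of min(u, 150)/150

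**Step 3. Percentage shown.** Assumed: constant hazard within the window. For a true 5% risk over the window, the expected crude percentage is the mean over children of 1 − 0.95^(observed days/window length). The last two columns are separate 5% scenarios.

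| Assumed start of dosing | After 150 d observed | Through 360 d observed | Through 150 d observed | Children with 360 d | True 5% after 150 d shows as | True 5% through 360 d shows as |
|---|---|---|---|---|---|---|
| 1 Oct 2021 | 15.5% | 50.4% | 99.2% | 0% | 0.8% | 2.6% |
| 23 Jun 2021 | 39.1% | 64.3% | 99.6% | 0% | 2.0% | 3.2% |
| 1 Jan 2021 | 67.3% | 80.8% | 99.8% | 38.6% | 3.4% | 4.1% |
| 1 Aug 2020 | 76.9% | 86.5% | 99.9% | 56.8% | 3.9% | 4.3% |

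The through-360-day figure is less distorted if events come early. With dosing from 23 June 2021 and 4 of the 5 points assumed to fall by Day 150, 5% shows as 4.4%, while the remaining 1.0% after Day 150 shows as 0.4%.

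**Step 4. Second interim.** Assumed: lock when the last child reaches Day 151, uniform accrual over T days. The share of children who can have 360 days is max(T − 210, 0)/T. For T = 180, 365 and 540 this gives 0%, 42% and 61%, with 43%, 71% and 81% of the after-150-day window observed.

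**Step 5. Zero events in 30 children (the planned interim minimum).** Taken as a completed window, 0/30 has an exact 95% upper limit of 11.6%. With dosing from 23 June 2021, the mean time observed after Day 150 is 82.05 d, so child-time is 30 × 82.05/365.25 = 6.74 child-years. The Poisson upper limit is 3.689/6.74 = 0.547 per child-year, or 1 − exp(−0.547 × 210/365.25) = 27% over 210 days at a constant rate. The same sum gives about 15% with dosing from August 2020 and about 55% from October 2021.

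**The case against.** **The interim table specifications are redacted.** SAP 5.1 and 5.2 place them in a separate document. A reader might infer that no rule exists. The documents support only that none is visible, because that document may drop the later windows or restrict their denominators. This stands and limits the claim.

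**The consequence is small.** The protocol's efficacy endpoint runs only through 150 days, no formal comparison is planned, the summaries are described as based on observed events, and the cut-off date is printed on the outputs. SAP 4.2.1 also reports how many children completed Day 151 and Day 361. All of this stands. It lowers the weight of the point, but a disposition count elsewhere does not correct a percentage with the wrong denominator.

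**HRU may not be affected.** SAP 4.2.6.4 asks for percentages over the same windows, so a reader might infer the same bias. But the interim data listed in Protocol 4.8.8 and SAP 5.1 are safety, PK, ADA and efficacy. In addition, the HRU summaries are repeated by Table 1 endpoint, so the denominator could be children with the event rather than all dosed children. The documents do not settle it.

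**The number of analyses is consistent.** A reader might infer that the two planned analyses in SAP 4.1 are out of date. SAP 5.2 and SAP 6 say the second interim was not pre-planned, so two planned analyses plus one unplanned one agree. The missing second cut-off date is at most a clarification: the amendment history shows that the first date was itself added later, on 15 June 2022.

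**The size is assumed.** Starting dosing on 23 June 2021 leaves out earlier Japanese children, so neither the 2.0% nor the 27% should be quoted alone. This stands, and the whole range is needed.

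**Conclusion.** The point holds for the after-150-day and through-360-day RSV LRTI and RSV hospitalization percentages at the two interims, on the readable text. Followed as written, those percentages are biased low. The direction is certain wherever some windows are open and the denominator is all dosed children. The size is not: a true 5% after-150-day risk would show as 0.8% to 3.9% at the first interim, depending on assumed dosing dates and a constant hazard. RSV is seasonal, so the real distortion could be larger or smaller.

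A reader might infer that the study's efficacy result is compromised. It is not. The secondary through-150-day endpoint is at least 99% observed in every scenario, the analysis is descriptive, and at the final analysis only dropout and death remain.

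The conflict over the first-interim population is plain on the page and needs correcting whatever the redacted specifications say. Overall the point is minor.

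**What to change.** 1. In SAP 4.2.5.3 or 5.1, state for each interim that the after-150-day and through-360-day RSV percentages are either omitted, or replaced by event counts with the number of children at risk at the start of the window, the number who completed it, and first events per child-time. An exact Poisson interval is optional. If the redacted specifications already do this, one sentence saying so is enough. Apply the same rule to HRU percentages only if they are produced at an interim with all dosed children as the denominator.

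2. Use one phrase for the first-interim population across the Protocol synopsis, Protocol 4.8.1 and 4.8.8, and SAP 4.1 and 5.1. Reconcile SAP 4.2.1, which ties the efficacy evaluation to completing Day 151, with Protocol 4.8.6, which takes all dosed children.

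3. As an optional clarification, give the second interim its own cut-off date in SAP 4.1.5.

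The cost is a few sentences and, if the later windows are kept, a few table rows. No new data are needed, and the through-150-day and final analyses keep their form.

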#### **Analysis of incidence of medically attended LRTI due to RT-PCR-confirmed RSV**

An analysis window which captures all relevant respiratory samples that linked to respiratory illness events will be defined prior to database lock and the decision made will be documented. In addition, deaths that can be demonstrated as caused by RSV (by autopsy or clinical history and virologic evidence) will also be considered as medically attended RSV LRTI events.

The incidence of medically attended RSV LRTI (inpatient and outpatient) through 150 days post dose will be summarized, and a listing of subjects with medically attended RSV LRTI will also be provided. For subjects with multiple medically attended RSV LRTI events, only the first occurrence will be used in the summary.

In addition, the incidence of medically attended RSV LRTI that occurred after 150 days post dose, and through 360 days post dose will be summarized.

The incidence of medically attended RSV LRTI by subtype (RSV A or RSV B) through 150 days post dose, after 150 days post dose, and through 360 days post dose will be summarized.

#### **Analysis of Incidence of RSV hospitalization**

The events of “RSV hospitalization” are a subset of “medically attended RSV LRTI,” and RSV test results are obtained from central laboratory. In addition, deaths that can be

demonstrated as caused by RSV (by autopsy or clinical history and virologic evidence) will also be considered as medically attended RSV hospitalization events.

The incidence of RSV hospitalization through 150 days after dosing will be summarized. For subjects with multiple RSV LRTI hospitalizations, only the first occurrence will be used in the analysis. RSV LRTI hospitalization will also be summarized by RSV subtype (RSV A or RSV B). This summary will be based on observed events and data summary will be presented through 150 days post dose, after 150 days post dose and through 360 days post dose.

#### **Other efficacy analyses**

An overall summary of subjects with any medically attended LRTI (protocol-defined or non-protocol-defined) or hospitalization due to any respiratory illness will be presented, and a listing capturing all relevant information will also be provided. The mapping between the AE terms and LRTI or non-LRTI will be finalized before the database lock. In this summary, a subject is reported only once even though he or she might have multiple events in the reporting period. In that occasion, the event with the highest severity level will be reported. The rules to define severity among multiple LRTI events for a subject are as follows: protocol-defined > non-protocol-defined, RSV > non-RSV, and hospitalization > outpatient. The rules to define severity among multiple hospitalizations due to any respiratory illness are as follows: LRTI > non-LRTI, RSV > non-RSV. Incidence of all medically attended LRTI will be summarized by protocol-defined LRTI (RSV or non-RSV) and non-protocol-defined LRTI (RSV or non-RSV) with each further broken down by hospitalization or outpatient status.

A listing will be presented for each of the elements used to evaluate for the case definition of any medically attended LRTI (see [Appendix 1](#) of this SAP). These elements include the following: rhonchi, rales, crackles, wheeze, increased respiratory rate, hypoxemia, acute hypoxic or ventilatory failure, new onset apnea, nasal flaring, retractions, grunting, dehydration due to respiratory distress. In this summary, a subject is reported once even though he or she might have the element multiple times during the reporting period.

[figure not shown]
For all medically attended LRTI events, RSV status (positive, negative or not done) will be summarized by central RT-PCR or local testing results. The proportion of each category will be calculated based on the total number of LRTI events.

Apart from the medically attended RSV LRTI and medically attended RSV LRTI with hospitalization efficacy endpoints (listed as first two endpoints in [Table 1](#)), additional four endpoints are also added to conduct similar analyses as mentioned above for exploratory purposes.

**Table 1 Population for medically attend RSV respiratory illness**

Type of Endpoint	Endpoint	Protocol definition of LRTI	RSV test result	Investigators assessment of LRTI/URTI	Setting of care
Secondary Efficacy	MA RSV LRTI	Protocol defined	Positive (central RT-PCR)	LRTI	Inpatient or outpatient
Secondary Efficacy	MA RSV LRTI with hospitalization	Protocol defined	Positive (central RT-PCR)	LRTI	Inpatient

CCI

[figure not shown]
All above stated summaries will be based on observed events and data summary will be presented through 150 days post dose, after 150 days post dose, and through 360 days post dose.

Adverse events associated with all medically attended RSV LRTI will be summarized, as well as categorized by the MedDRA SOC and PT. Summaries will be presented through 150 days post dose, after 150 days post dose, and through 360 days post dose.

[figure not shown]
To evaluate the impact of ADA on efficacy, MA LRTI and MA LRTI with hospitalization will be summarized by ADA post-baseline status (ie, at least one post-baseline ADA positive or not through 360 days post dose).

